# 1. SUMMARY

## 1.1. Type of Request

A two cohort phase II, open-label, non-randomized, international multi-centre study of an IMP licensed but used for new indication.

## 1.3. Study Title

Phase II Clinical Trial of Pazopanib to evaluate the activity and tolerability in patients with advanced and/or metastatic liposarcoma who have relapsed following standard therapies or for whom no standard therapy exists.

## 1.11. Study phase and design

A two cohort Phase II, open-label, non-randomized, multi-centre study with 5 centres in Spain and 5 centres in Germany. Patients will receive oral Pazopanib, 800mg once daily and treatment will continue until disease progression, development of unacceptable toxicity, non-compliance, withdrawal of consent by the patient or investigator decision.

## 1.12. Primary Objective

The primary objective of this study is to evaluate the activity of Pazopanib in patients with advanced and/or metastatic liposarcoma by means of progression-free survival (PFS) assessed 12 weeks after start of treatment. (According the RECIST criteria 1.1 and central radiology review).

## 1.13. Disease under investigation

Advanced and/or metastatic liposarcoma

**1.14. Primary endpoint**

The primary efficacy endpoint for this study is progression-free survival (PFS) assessed 12 weeks after start of treatment. (According the RECIST criteria 1.1 and central radiology review).

**1.15. Patients to be included**

Patients with advanced and/or metastatic liposarcoma who have relapsed following standard therapies or for whom no standard therapy exists will be included.

**1.16. Sample Size**

74 patients (maximum of 37 patients in 2 different cohorts)

**1.17. Treatment duration**

Treatment will continue until disease progression, development of unacceptable toxicity, non-compliance, withdrawal of consent by the patient or investigator decision.

**1.18. Planned trial periods**

**Start date:** Third quarter 2012.

**First subject first visit (FSFV):** Fourth quarter 2012.

**Total duration of recruitment period:** 30 months.

**Last subject first visit (LSFV):** Second quarter 2015.

**Follow-up period:** 12 months.

**End of study date:** Last patient last visit. Estimated second quarter 2016.

## LIST OF ABBREVIATIONS AND DEFINITION OF TERMS

ACTH	Adrenocorticotrophic hormone
AE	Adverse event
ALT	Alanine aminotransferase
ANC	Absolute neutrophil count
aPTT	Activated PTT
AST	Aspartate aminotransferase
BP	Blood pressure
C24	Concentration at 24 hr following single-dose administration
CR	Complete response
CRF	Case Report Form
CrCl	Creatinine Clearance
CT	Computerized tomography
CYP	Cytochrome P450 (subtypes 3A, 3A4, 2D6)
DBP	Diastolic blood pressure
DNA	Deoxyribonucleic acid
DVT	Deep vein thrombosis
ECG	Electrocardiogram
ECO	Echocardiography
ECOG PS	Eastern Cooperative Oncology Group Performance Status
EIAC	Enzyme-inducing anticonvulsants
FDA	Food and Drug Administration
Flt-3	Fms-like tyrosine kinase-3
FU	Follow up
GCP	Good Clinical Practice
GISG	German Interdisciplinary Sarcoma Group
GSK	GlaxoSmithKline
HIF-1a	Hypoxia-inducible factor-1a
HRT	Hormone Replacement Therapy
IC 50	Half-maximal inhibition
IDMC	Independent Data Monitoring Committee
IND	Investigational New Drug
INR	International normalized ratio
IRB/IEC	Institutional Review Board/Independent Ethics Committee
ITT	Intent-to-treat
TKI	Tyrosine Kinase Inhibitor
LD	Longest diameter
LVEF	Left Ventricular Ejection Fraction

LLN	Lower Limit of Normal
MRI	Magnetic resonance imaging
msec	Millisecond(s)
MTD	Maximum tolerated dose
mTOR	mammalian Target of Rapamycin
MUGA	Multi-Unit Gated Analysis
NCI-CTCAE v4.0	National Cancer Institute-Common Toxicity Criteria for Adverse Events Version 4.0
OS	Overall survival
PD	Progressive disease
PDGF	Platelet-derived growth factor
PDGFR	Platelet-derived growth factor receptor
PFS	Progression-free survival
PR	Partial response
PTT	Partial thromboplastin time
QD	Once daily
QTc	Corrected QT interval
RAP	Report and analysis plan
RCC	Renal cell carcinoma
RECIST	Response Evaluation Criteria In Solid Tumors
SAE	Serious adverse event
SBP	Systolic blood pressure
SD	Stable disease
SPC	Summary of Product Characteristic
STS	Soft Tissue Sarcoma
T3	Triiodothyronine
T4	Thyroxine
TSH	Thyroid-stimulating hormone
ULN	Upper limit of normal
VEGFR	Vascular endothelial growth factor receptor
µM	Micromolar

### 3. GENERAL INFORMATION

#### STUDY IDENTIFICATION

**TITLE:** Phase II Clinical Trial of Pazopanib to evaluate the activity and tolerability in patients with advanced and/or metastatic liposarcoma who have relapsed following standard therapies or for whom no standard therapy exists.

**PROTOCOL NUMBER:** GEIS-30

**N° EudraCT:** 2012-002745-38

#### ***3.1. Clinical Trial Type***

A two cohort phase II, open-label, non-randomized, international multi-centre study of an IMP licensed but used for new indication.

### ***3.8. Planned trial periods***

**Start date:** Third quarter 2012.

**First subject first visit (FSFV):** Fourth quarter 2012.

**Total duration of recruitment period:** 30 months.

**Last subject first visit (LSFV):** Second quarter 2015.

**Follow-up period:** 12 months.

**End of study date:** Last patient last visit. Estimated Second quarter 2016.

## 4. RATIONALE AND OBJECTIVES

### 4.1 BACKGROUND AND RATIONALE

Soft tissue and bone sarcomas are rare malignant tumors, which encompasses a large family of more than 50 histologically distinct tumor subtypes, all of which share a putative mesenchymal origin. In the case of soft tissue sarcomas (STS) surgical excision is the mainstay of treatment, but despite curative surgery, around half of patients develop distant metastases and die from disease. Few therapeutic approaches are currently available to patients with unresectable, locally advanced, or metastatic STS and only anthracyclines, ifosfamide and trabectedine have shown activity, with response rates of 20–40% in previously untreated patients. Recent and ongoing trials have investigated a variety of combination chemotherapeutic regimens (variously employing ifosfamide, doxorubicin, gemcitabine, temozolamide, vincristine, cisplatin, and dacarbazine, among others) as well as targeted therapies, which in some cases have yielded improvements in response rate but which have had little impact on survival. No other medical option is currently available, and the median survival of patients with soft-tissue sarcoma with non-resectable metastases is around 12-15 months, and approximately 8 months after second line chemotherapy.

Liposarcomas are STS which account for at least 20% of all STS in adults. They can be further classified into 3 histologically and biologically different subtypes: well-differentiated liposarcoma/de-differentiated liposarcoma (ALT-WD), myxoid or round cell liposarcoma and pleomorphic liposarcoma.

ALT-WD liposarcomas are locally aggressive rarely metastasising tumors characterized by ring or giant marker chromosomes on the cytogenetic analysis and by amplification of the 12q13-21 region on FISH (MDM2, CDK4 and HMGIC). They account for about 40% of liposarcomas with a 5 year OS around 80%. In a series of WD/DD treated with several regimens response rate was 12.5% OS 15 months and median PFS 3.6 months(95 CI: 3.3-5.9)

Mixoid /round cell liposarcoma accounts for 45-50% of all liposarcomas. They tend to metastasise to unusual soft tissue and bone locations. High histologic grade with more than 5% of round cell component is associated with a 5-year OS of 50% approx. They are characterized by t(23;16)(q13-14;p11) which leads to the fusion of CHOP and TLS genes.

Pleomorphic liposarcoma accounts for approximately 5-10% of all liposarcomas, characterized by high grade features with frequent and early lung metastasis and cytogenetically by high chromosome counts and complex structural rearrangements.

VEGF is expressed in many STS in which increased expression is associated with higher grade and worse prognosis.

Pazopanib is an oral angiogenesis inhibitor that targets mainly VEGFR, PDGFR and c-kit. Recently the results of a phase II trial of Pazopanib in STS have been published. It was a four-cohort 2-stages study. The liposarcoma stratum was closed after the first stage because of a PFS at 12 weeks of 17% (3 out of 17 patients did not progressed after 12 weeks). After central pathologic review, 2 other patients initially classified as other STS were found to have liposarcoma with stable disease at 12 weeks (5/19: 26% PFS12w), thus fulfilling criteria for cohort expansion. Phase II study had been completed and in phase III study patients with liposarcomas were excluded so therefore data on the liposarcoma cohort are inconclusive.

Furthermore the positive results of the phase III study PALETTE have been recently communicated, encouraging this treatment in other sarcomas: progression-free survival (PFS) per independent review was significantly prolonged with Pazopanib (median: 4.6 vs 1.6 months; HR=0.31, 95% CI 0.24-0.40; P<0.0001). The interim analysis for overall survival shows a statistically non-significant improvement of Pazopanib vs placebo (median: 12.5 vs 10.7 months, HR=0.83, 95% CI 0.67 – 1.11 p=0.25) .

Soluble factors associated with efficacy and toxicity of Pazopanib in these patients had been also reported . Decreases in VEGFR2 and increase in PIGF were both associated with toxicity (HTA and TSH elevation) and poorer prognosis.

## **4.2 Rationale for the Pazopanib Dose**

The Pazopanib dose to be used in this study is 800 mg daily, based on the following consideration:

Pazopanib 800 mg once daily is the recommended monotherapy dose based on clinical and preclinical results. Once daily doses of 50 mg to 2000 mg Pazopanib were investigated in the “First Time in Human”, Phase I Study VEG10003. Increases in the Pazopanib dose above 800 mg once daily when administered in the fasted state did not result in a consistent increase in systemic exposure at steady state. Therefore, no further benefit is expected at Pazopanib doses above 800 mg once daily.

Pharmacodynamic data indicate that Pazopanib, at a monotherapy dose of 800 mg once daily, results in effects consistent with inhibition of the VEGF receptors it was designed to target. Concentration-effect relationships were observed between trough plasma Pazopanib concentrations and the development of hypertension in Study VEG10003 and the percent change from baseline in sVEGFR2 nadir in Study VEG102616. The trough plasma Pazopanib concentrations associated with one-half the maximal effect (EC50) in both concentration-effect relationships were similar (21.3 µg/mL and 15.3 µg/mL) and demonstrate that there is a consistent inhibition of VEGF receptor(s) in subjects with cancer when plasma Pazopanib concentrations are maintained above 15 µg/mL. The plasma Pazopanib EC50 values for biologic effects observed in the clinical studies are similar to the plasma concentration of 40 µM (17.5µg/mL) required for optimal inhibition of VEGFR-2 phosphorylation in mice [GSK Report RH2003/00005/00].

Progression Free Survival (PFS) in subjects with renal cell cancer in Study VEG102616 was compared between subjects whose trough plasma Pazopanib concentrations (Cmin) at Week 4 were above or below selected threshold values. The deciles of the observed Cmin values were selected as threshold values so that approximately equal numbers of subjects were included in each Cmin interval. Subjects with a Cmin at Week 4 above the threshold values had significantly better PFS, compared to the remaining subjects, when the threshold concentrations steady were 12.6µg/mL, 17.4µg/mL, and 20.6µg/mL. Use of thresholds higher than 21µg/mL did not result in a significant improvement in PFS between patients with Cmin values above and below the threshold. Patients with Cmin concentrations above 20.6µg/mL also had significantly better response rate and tumor shrinkage than the remaining patients.

Pazopanib C24 at steady state was greater than 15µg/mL in 93% of subjects who received 800 mg once daily in Study VEG10003. Individual subjects receiving Pazopanib doses below 800 mg once daily can achieve plasma concentrations over 15µg/mL, albeit at a lower frequency compared with what is observed at 800 mg once daily. Therefore, the pharmacokinetic and pharmacodynamic results across clinical studies demonstrate that

Pazopanib 800 mg once daily results in plasma concentrations that provide optimal biologic effects associated with VEGFR inhibition in the greatest proportion of subjects.

### **4.3. Study Objectives**

#### **4.3.1. Primary Objective:**

The primary objective of this study is to evaluate the activity of Pazopanib in patients with advanced and/or metastatic liposarcoma by means of progression-free survival (PFS) assessed 12 weeks after start of treatment. (According the RECIST criteria 1.1 and central radiology review).

#### **4.3.2. Secondary Objectives:**

- Overall progression-free survival (median PFS)
- Objective tumor response (confirmed complete response [CR] and partial response [PR] using modified Response Evaluation Criteria in Solid Tumors [RECIST] 1.1)
- Time to onset of response
- Duration of response
- Overall survival (OS)
- Clinical benefit rate (CBR)
- Growth Modulation Index (GMI).
- Safety profile (according CTCAE, version 4.0)

#### **4.3.3. Translational Study Objectives**

##### **PRIMARY OBJECTIVES:**

- To evaluate the influence of the angiogenic status of the tumor on the response to Pazopanib.
- To evaluate the serum profile of serum cytokine markers as indicator of response to Pazopanib.

##### **SECONDARY OBJECTIVES:**

- To evaluate microvessel density (MVD) and p53, MDM2, PTEN and VEGF/PDGF pathways by IHQ expression and their correlation with prognosis as well as their role as predictive factors to treatment with Pazopanib (Response, PFS and OS).
- To evaluate serum levels of several angiogenic factors/cytoquines using Luminex XMAP Technology at baseline, after the first 3 weeks of treatment, at maximum response and at progression and their predictive value for survival and response to treatment: VEGF-A, PIGF-1, SDF-1 alpha (CXCL12), TNF alpha, IL-8, IL-6, PDGF –beta, HGF, E- Selectine, ICAM1, MMP-9 and FGFb.
- To analyse PIK3CA mutations in order to demonstrate if those liposarcomas with PIK3CA mutations defines a subgroup of patients with differential response to Pazopanib.

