### **5.7 Response evaluation**

Informed consent must be obtained prior to start of the specified screening window. Procedures conducted as part of the subject's routine clinical management (e.g., blood count, imaging study such as bone scan) and obtained prior to signing of informed consent may be utilized for screening or baseline purposes provided these procedures are conducted as specified in the protocol.

Response evaluation will be done by means of RECIST version 1.1 criteria.

Imaging Studies: CT Scan or MRI will be used for response evaluation. Disease should be captured and target/non-target identified at baseline, CT scan or MRI as appropriate. Subsequently, imaging studies required to investigate known disease should be performed on week 7, on week 12 and every 8 weeks thereafter. Imaging methods will be employed consistently during the course of each patient's evaluation during the study. After discontinuation of protocol treatment, patients who have not progressed will still be re-evaluated every 8 weeks, unless they have started a new anti-cancer therapy.

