### **5.8. Translational sub-study**

For those patients that have consented for the participation in the translational sub-study, the biological samples will be collected as follows:

- Paraffin-embedded samples from original tumor and if clinically acceptable (ex. superficial or easily accessible locations), tumour biopsy at study entry.
- Serum from peripheral blood will be performed (4 per subject):
  1. Within 72 hours prior starting the treatment (basal).
  2. Within 72 hours after the first 3 weeks of treatment (Day 22).
  3. Within 72 hours after radiological response is documented.
  4. Within 72 hours after progressive disease is documented.

Translational sub-study will be carried out by:

[REDACTED]

[Redacted]

All samples will be shipped codified as is specified in the detailed tumour collection and shipment procedures. For more information regarding translational sub-study, please see section 13 of this protocol.

For sending the biological samples, please contact to:

[Redacted]

An additional document will be provided in the Investigator Site File with detailed biological sample collection and shipment procedures.

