### STUDY OF BIOMARKERS:

Paraffin-embedded samples from 74 original tumors and if clinically acceptable (ex. superficial or easily accessible locations), tumour biopsy at study entry will be collected and the following analysis will be carried out:

- Microvessel density on full sections of the tissue.
- Immunohistochemical profile of angiogenic markers and p53, MDM2 and PTEN.
- Quantitative RT-PCR of a panel of angiogenic markers.

Serum from peripheral blood will be performed (4 per subject):

1. Within 72 hours prior starting the treatment (basal).
2. Within 72 hours after the first 3 weeks of treatment.
3. Within 72 hours after radiological response is documented.
4. Within 72 hours after progressive disease is documented.

Methodology:

a) Microvessel density and immunohistochemistry: Full sections of paraffin-embedded material will be stained with anti-CD34 or anti-CD31 and evaluated using a light microscope and specific software for measuring microvessels with no muscular walls.

Tissue microarrays (TMA) will be constructed containing at least two cores (1.0 mm in diameter) from each tissue sample.

At least the following antibodies will be tested: VEGF, PDGF, VEGFR-1 (flt-1), VEGFR-2 (flk-1/KDR), PDGFR-alfa, PDGFR-beta, HIF-1, TSP-1, VE-cadherin, p53, MDM2 and PTEN.

Additional tests could be considered depending of new findings or evidences in the field of tumor angiogenesis.

b) RT-PCR Low density arrays for the expression of angiogenic factors: We will perform an RNA extraction from paraffin embedded material and an RT-PCR low density expression array containing 94 angiogenesis-related genes will be analysed. These arrays include known angiogenesis growth factors like VEGF, and known matrix derived inhibitors such as endostatin. Additionally, the panel contains markers and targets for angiogenesis and lymphangiogenesis.

List of genes included:

- Angiogenic growth factors (28): ANG, ANGPT1, ANGPT2, ANGPT4, CSF3, CTGF, CXCL12, ECGF1, EDIL3, EPHB2, FGF1, FGF2, FGF4, FST, GRN, HGF, IL8, LEP, MDK, PDGFB, PROK1, PTN, TGFA, TGFB1, TNF, VEGF, VEGFB, VEGFC.
- Angiogenesis inhibitors (37): ADAMTS1, ANGPTL1, BAI1, CHGA, COL15A1, COL18A1, COL4A1, COL4A2, COL4A3, CXCL10, CXCL2, F2, FBLN5, FGA, FLT1, FN1, HSPG2, IFNB1, IFNG, IL12A, ITGA4, LECT1, PF4, PLG, PRL, SEMA3F, SERPINB5, SERPINC1, SERPINF1, THBS1, THBS2, TIMP2, TIMP3, TNFSF15, TNMD, TNNI1, VASH1.

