- Angiogenesis markers (10): AMOT, ANGPTL2, ANGPTL3, ANGPTL4, CEACAM1, HEY1, ITGAV, PECAM1, PGK1, XLKD1.
- Angiogenesis targets (13): EDG1, ENPP2, FLT3, FLT4, ITGB3, KDR, KIT, NRP1, NRP2, PDGFRA, PDGFRB, TEK, TIE1
- Lymphangiogenesis markers (5): CD44, CDH5, FIGF, FOXC2, PROX1
- Controls (2): 18S, GAPDH

c) Serum cytokine markers: The Luminex technology will be employed for the analysis of 12 cytokines [VEGF-A, PlGF-1, SDF-1 alpha (CXCL12), TNF alpha, IL-8, IL-6, PDGF-beta, HGF, E-Selectine, ICAM1, MMP-9 and FGFb].

d) Analysis of PIK3CA mutations: DNA extraction, amplification of exons 4, 7, 9 and 20 of PIK3CA by PCR and direct sequencing will be performed.

[figure not shown]
The proposed biomarker study includes analysis of tumor tissue at diagnosis and serum cytokines and growth factors at different phases within the treatment schedule. In the case of serum, the kinetic profile of each biomarker will be considered (decreased, constant, increased). All analysed parameters will be correlated with: Progression-free survival (PFS) assessed 12 weeks after start of treatment (According the RECIST criteria 1.1); median PFS; objective tumor response; overall survival and histopathological parameters. For the statistical analysis, we will use binary variables reflecting the positivity status of the measures (yes or no; presence/absence). Association with histopathological parameters, and objective tumor response, all categorical, will be also assessed using a chi-square test to determine homogeneity or linear trend for ordinal variables. The significance level will be set at 5%. To study the impact of the histological, immunohistochemical and molecular factors on progression-free survival (PFS) and overall survival (OS), the Kaplan-Meier proportional risk test (log rank) will be used. Evidence of the relative risk for each patient will be also provided by means of a Cox proportional hazards model using stepwise selection to identify the independent predictors of poor outcome.

We do not plan to use multivariate analysis to analyse biomarkers. Standard pre-post univariate tests will be used instead.

For the kinetic profile of the serum biomarkers, each variable will be considered as continuous. A correlation between the growth factor or cytokine levels with the different points of the treatment schedule will be considered and the slope value will be used in

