order to distinguish those cases with no change, negative or positive trend. The threshold will be calculated after considering the behaviour of the whole series. The slope value will be considered from baseline and using the nonparametric Wilcoxon signed-rank test. However other analysis will be undertaken depending of the behaviour of the measures.

For sending the biological samples, please contact to:

An additional document will be provided in the Investigator Site File with detailed biological sample collection and shipment procedures.

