1.16.3. Translational objectives

PRIMARY OBJECTIVES:

- To assess the influence of the tumor's angiogenic state on the response to Pazopanib.
- To assess the profile of serum cytokines as an indicator of response to Pazopanib.

SECONDARY OBJECTIVES:

- To assess the density of microvessels (DMV) and the pathways of p53, MDM2, PTEN, and VEGF / PDGF by immunohistochemistry, their correlation with prognosis, and their role as predictors of treatment with Pazopanib (response, PFS, and OS).
- Assess serum levels of various angiogenic factors / cytokines using Luminex XMAP Technology at baseline, after the first 3 weeks of treatment, at the time of maximum response and in tumor progression and its predictive value for survival and response to treatment: VEGF-A , PIGF-1, SDF-1 alpha (CXCL12), TNF alpha, IL-8, IL-6, PDGF-beta, HGF, E-Selectin, ICAM1, MMP-9 and FGFb.
- Analyze the presence of mutations in PIK3CA to demonstrate whether those liposarcomas with mutations in PIK3CA define a subgroup of patients with a different response to Pazopanib.

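### Serum samples triggered by response or progression are planned as predictors of response, PFS and OS, with no landmark or timing rule

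*Protocol*

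**What the plan says.** Protocol 4.3.3 lists, as a secondary translational objective, twelve serum factors measured at baseline, after three weeks, "at maximum response and at progression and their predictive value for survival and response to treatment". Protocol 13 repeats this, and SAP 1.16.3 has it as "at the time of maximum response and in tumor progression and its predictive value for survival and response to treatment".

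Protocol 5.8, the footnotes to the table of assessments (8.1), item 12 of 8.2 and Protocol 13 set the draws. Samples 1 and 2 have fixed times: before treatment, and within 72 hours after day 22. Sample 3 is taken "Within 72 hours after radiological response is documented" and sample 4 "Within 72 hours after progressive disease is documented". The grid of the table of assessments marks serum only before treatment and at week 3.

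For the analysis, Protocol 13 classes each serum marker's kinetic profile as falling, constant or rising, using its levels across the points of the treatment schedule. On the slope it says: "The slope value will be considered from baseline and using the nonparametric Wilcoxon signed-rank test". The cut for the slope is to be chosen after looking at the whole series. The same section relates every analysed parameter to 12-week PFS, median PFS, objective response and OS. Protocol 10.4 counts PFS and OS from treatment initiation.

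I found no landmark, no time-dependent covariate, no restriction of prediction to the fixed-time samples, and no rule for patients without sample 3 or 4. The SAP as supplied repeats the objective and gives no method for it.

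**The concern.** A predictor has to be measurable before the outcome, and in every patient at risk of it. Two of the four serum samples fail this. Sample 3 is drawn because a response was documented, and sample 4 because the PFS event was documented.

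A kinetic profile that includes either sample therefore carries information about when, or whether, the outcome occurred. It could associate with response or PFS even if the marker has no prognostic content. For OS, a patient must live long enough to respond or progress before giving the sample, while survival is counted from treatment start.

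At stake is whether any cytokine reported as predictive from this study could be believed.

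**Working it through.** **No stated figure to reproduce.** The biomarker plan gives no sample size or power. The only design figure is the Simon design of Protocol 10.4 (17 then 37 patients, continue on 4 or more successes, positive on 11 or more, P0 = 20%, P1 = 40%). It reproduces: exact type I error 0.0948, power 0.9033. This point does not touch it.

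**Timing, sample by sample.** Scans are "performed on week 7, on week 12 and every 8 weeks thereafter" (Protocol 5.7).

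| Sample | Trigger | Against response | Against PFS, 12-week PFS | Against OS from treatment start |
|---|---|---|---|---|
| 1, baseline | fixed | valid | valid | valid |
| 2, day 22 plus up to 72 h | fixed, before the first scheduled scan | valid from a landmark | valid from a landmark | valid from a landmark |
| 3 | documented response | drawn after the outcome | only responders who lived progression-free to response | immortal time, selection |
| 4 | documented progression | exists only in progressors | drawn after the outcome | immortal time, selection |

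**How many patients have sample 3.** The only response rate given for a matching histology is 12.5%, from a well-differentiated/dedifferentiated series on several regimens (Protocol 4.1).

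- One cohort: 0.125 × 37 = 4.6, about 5 patients.
- Both cohorts: 0.125 × 74 = 9.25, about 9.
- Assumed rates of 5% and 20%: 0.05 × 74 = 3.7 and 0.20 × 74 = 14.8, so about 4 to 15.

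**Simulated size of the bias for sample 4.** The marker has no prognostic value. Settings:

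- 74 patients, 1,000 trials per scenario, log-rank at two-sided 5% (the protocol gives 5% but no sidedness), groups split at the sample median, scans on the protocol schedule.
- Median PFS 3.6 months × 52/12 = 15.6 weeks (Protocol 4.1), or 8 weeks (assumed). Median post-progression survival 35 or 27 weeks (assumed).
- Independent noise of 1 SD at each draw. Every patient progresses and gives sample 4; no censoring, no death before progression.
- Simulation error near 5%: √(0.05 × 0.95 / 1000) = 0.7 points.

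| Analysis | Marker behaviour | False positives, PFS | False positives, OS |
|---|---|---|---|
| Slope: baseline, week 3, progression | noise only | 16% | 7.5% |
| | 0.5 SD step at progression | 56% | 11% |
| | 1 SD step | 92–95% | 15–31% |
| Change, baseline to progression | noise only | 4.7% | 6.2% |
| | 1 SD step | 5.6–5.8% | 4.8–5.2% |
| | drift 0.05 SD/week | 68–98% | 10–31% |
| Change, baseline to week 3, from a week-3 landmark | all scenarios | 4.4–5.7% | 4.8–7.2% |
| Change to progression, survival from progression | all scenarios | – | 4.9–6.6% |

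**Why the slope misbehaves.** A slope divides by elapsed time, so patients with long PFS have slopes close to zero whatever the marker does. A cut taken from the sample then tends to put them on the same side, and a common step at progression looks steep in early progressors and shallow in late ones. A check with the cut at zero brought the noise and 1 SD-step cases back close to nominal. The result therefore depends on the threshold as well as on the marker, and the protocol leaves the threshold to be chosen from the data.

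**The case against.** The strongest reply is that the plan never states the faulty analysis. The test named for the slope is a paired signed-rank test, and Protocol 13 says standard pre-post univariate tests will be used for biomarkers. The log-rank test is named for histological, immunohistochemical and molecular factors, not for serum slopes. On that reading samples 3 and 4 serve only within-patient description, which is legitimate. This partly stands: no sentence enters either sample into a log-rank or Cox model. It does not remove the point. The objective assigns predictive value to all four times, Protocol 13 relates every parameter to four outcomes, and a paired test of change cannot establish prediction.

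A reader might also say the sub-study is exploratory, is published separately, and allows other analyses depending on the data. That stands as a limit on importance, not as a remedy.

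Third, the primary translational objective speaks of serum as an indicator of response, and a level measured at response and compared with the same patient's baseline can be a fair concurrent marker. That stands too, so I do not call the answer to that objective circular as a whole. The fault lies in the predictive use.

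**Conclusion.** The point holds. Followed as written, the plan relates samples triggered by the outcome to that outcome, and nothing in either document prevents it.

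Two stronger readings are tempting, and the documents do not support them:

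- **The outcome has already happened in every comparison.** That is literal only for sample 3 against response and sample 4 against PFS or 12-week PFS. Both samples come before death, so for OS the fault is immortal time and selection.
- **Any slope using sample 3 separates responders by construction.** Having the sample identifies a responder; the slope values need not differ.

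The size is uncertain. The figures above concern sample 4 and rest on assumed marker behaviour, a median split and complete follow-up. They range from near nominal (simple change, no drift) to over 90% (slope with a 1 SD step, or change with a drift of 0.05 SD per week at the longer PFS). The 12.5% behind the sample-3 counts is not a pazopanib rate.

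The damage is confined to the translational objectives. The plan should be amended, but the trial's main conclusion does not depend on it.

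**What to change.** Amend Protocol 4.3.3 and 13 and SAP 1.16.3, and give the SAP a method for the serum objective:

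1. Predict response, 12-week PFS, PFS and OS only from the baseline level and the baseline-to-week-3 change.
2. For the change, count PFS and OS from a landmark at or after the end of the sample-2 window: day 22 + 72 hours = day 25, or the actual draw date. A day-22 landmark could precede the draw. The first scheduled scan is at week 7, so the change still precedes scheduled response assessment.
3. Use samples 3 and 4 for paired descriptive change, for survival counted from the draw, or as time-dependent covariates. Do not put them in a slope tested against outcomes counted from treatment start.
4. Fix the slope threshold, or the rule for it, before the outcome data are seen.
5. Reconcile the sampling time in the objective (maximum response) with the draw rule (after a response is documented). The two dates need not coincide.

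The cost is wording only; both fixed-time samples are already scheduled for consenting patients. The drawback is that patients who die or progress before the landmark leave that analysis, and their number should be reported.
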